Subjects: Participants will be 50 abstinent smokers, recruited during pregnancy, who provide written informed consent. We will recruit participants at the “Women’s Center” and its affiliated “Maternal Fetal Medicine High Risk” obstetrical clinics at Yale-New Haven Hospital (YNHH).

Inclusion Criteria: 1) Women with a history of smoking 5+ cigarettes per day that have achieved abstinence defined as no smoking or smoking less than 2 cigarettes per week by 32 weeks’ gestation during pregnancy by 32 weeks gestation; 2) aged 18 to 40 years; 3) able to speak and write English; 4) Edinburgh Postnatal Depression Scale (EPDS) score <10.

Exclusion Criteria: 1) Current substance abuse (e.g., alcohol, benzodiazepines, marijuana); 2) current major depressive disorder, minor depression or dysthymia, or history of any of these disorders in the last 6 months; 3) presence of an Axis I psychotic disorder; 4) plans to relocate out of the area 5) imminent incarceration; 6) planned inpatient hospitalization during study period.

Study Procedures

Overview: We propose to randomize 50 abstinent pregnant smokers to receive either the attentional retraining (AR) or control VP task. Participants will be asked to carry around a smartphone as they go about their daily lives for 2 weeks in their last month of pregnancy (Phase 1). The smartphone will sound an alert randomly during the day, at which time participants will be asked to respond to a short set of questions assessing subjective states; this will be followed by a request to complete the AR (or control) procedures. This same procedure will be repeated for 2 weeks immediately after delivery (Phase 2). Women will undergo a follow-

up visit 3 months after the end of Phase 2, and complete an unmodified VP and follow-up assessments. Given the COVID-19 pandemic screening will be done by phone and study visits, with the exception of Visit 1, will be done via Zoom. If/once it is appropriate to resume in person visits, participants will be offered the option of completing study visits in person at the research clinic or via Zoom.

Screening:

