Enrollment: We will follow eligible women that have not reached 32 weeks gestation at the time of screening and determine if they are still eligible for randomization. For women who are eligible for randomization we will perform an intake interview via Zoom (Visit 1, part a) that will include a review of study procedures and consent, and computer administered intake assessments (Table 1, Visit 1). Research staff will then coordinate to meet the participant before or after a routine prenatal visit to be provided with the study smartphone and home breath carbon monoxide monitor (Visit 1, part b). They will undergo a brief training on the use of the study program (including a baseline VP task) and the CO monitor on the smartphone. They will also be asked to provide a breath sample for carbon monoxide analysis. This entire in person visit will last 15 minutes. In the future, parts a and b of Visit 1 can be done as one once it is appropriate to conduct routine study visits in person.

At this point participants will be randomized to one of the two study conditions: attentional retraining (AR) or control. All enrolled women will be provided with educational materials to help them maintain abstinence from smoking.

Urn Randomization: Eligible women will be assigned to the two study conditions through "urn" randomization to ensure relatively equal allocation between treatment group (AR) and control

with respect to age and severity of nicotine dependence. In urn randomization, an algorithm modifies ongoing randomization probabilities based on the prior composition of treatment groups,⁵⁵ thus the allocation sequence is not pre-specified so allocation concealment is not necessary (see Sofuooglu et al. 2007).⁵⁶ To distribute age evenly over the two groups, a categorical variable will be created, 1= ages 18 to 30 and 2 for >30, because older women are more likely to achieve abstinence.¹ To explicitly require balance between groups with respect to level of dependence, a categorical variable will be created based on the number of cigarettes/day in the month before conception: 1=1-10; and 2=11 or more cigarettes on average, per day. Lastly, we will balance groups with respect to women with and without an anxiety disorder. Both the participant and the research assistant will be blinded as to the condition. Both the participant and the research assistant will be blinded as to the condition assignment.

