Exclusion Criteria: 1) Current substance use, with the exception of cannabis, if not used in a combustible form (e.g. edibles, teas, tinctures, etc.); 2) current major depressive disorder, minor depression or dysthymia, or history of any of these disorders in the last 6 months; 3) presence of an Axis I psychotic disorder; 4) plans to relocate out of the area 5) imminent incarceration; 6) planned inpatient hospitalization during study period.

The PI or research staff will screen potential subjects using the assessments described under study procedures. This includes modules from Addiction Severity Index, the Edinburgh Postnatal Depression Scale, the PhenX Toolkit measures (see Table 1). At intake, postpartum, subjects will complete the Kendler Social Support Inventory, Parenting Stress Index and a Substance Use Calendar. In addition, they will undergo an expired CO breath test to confirm smoking abstinence, at the time of enrollment (Visit 1, see Table 1 above). After assessments the PI will confirm whether or not the respondents met criteria outlined above.

4.a. Will email or telephone correspondence be used to screen potential subjects for eligibility prior to the potential subject coming to the research office? xYes No

4.b. If yes, will identifiable health information be collected during this screening process and retained by the research team? xYes No

5. Subject Classifications: Check off all classifications of subjects that will be invited to enroll in the research project. Will subjects, who may require additional safeguards or other considerations, be enrolled in the study? If so, identify the population of subjects requiring special safeguards and provide a justification for their involvement.

 Children Non-English Speaking Decisionally Impaired Healthy Prisoners Employees Students Fetal material, placenta, or dead fetus Economically disadvantaged persons Pregnant women and/or fetuses Females of childbearing potential

5.a. Is this research proposal designed to enroll children who are wards of the state as potential subjects?
 Yes No (If yes, see Instructions section VII #4 for further requirements)

SECTION VIII: CONSENT/ ASSENT PROCEDURES

1. **Consent Personnel:** Please see IRES-IRB.
2. **Process of Consent/Accent:** Describe the setting and conditions under which consent/assent will be obtained, including parental permission or surrogate permission and the steps taken to ensure subjects' independent decision-making.

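### The protocol wrongly states that an urn makes allocation concealment unnecessary, and it describes no procedure that would keep coming assignments hidden from whoever confirms eligibility

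*Combined protocol and SAP*

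**What the plan says.** Section V, item 3 sets the number to be randomised: "We propose to randomize 50 abstinent pregnant smokers to receive either the attentional retraining (AR) or control VP task". The Urn Randomization paragraph gives the aim of the method as "to ensure relatively equal allocation between treatment group (AR) and control". It explains that "an algorithm modifies ongoing randomization probabilities based on the prior composition of treatment groups", and continues in the same sentence: "thus the allocation sequence is not pre-specified so allocation concealment is not necessary".

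Three two-level factors enter the urn:
- age: "a categorical variable will be created, 1= ages 18 to 30 and 2 for >30"
- average daily cigarettes in the month before conception: "1=1-10; and 2=11 or more cigarettes on average, per day"
- presence or absence of an anxiety disorder

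The paragraph ends with the blinding statement: "Both the participant and the research assistant will be blinded as to the condition assignment". No other role is named.

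Section VII, item 3 (Inclusion/Exclusion Criteria) has the principal investigator or research staff do the screening, and then: "After assessments the PI will confirm whether or not the respondents met criteria outlined above".

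The Enrollment paragraph of Section V places the intake interview, the baseline visual probe task and the breath CO sample before randomisation. It does not place the investigator's confirmation of eligibility in that order.

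**The concern.** The sentence treats concealment as something only a pre-written list needs. Concealment is about people: those who decide whether a woman enters must not know, or be able to affect, the arm she would receive. An urn with no list can still fail this in two ways. Its state can be used to work out the likelier arm, or its result can be seen before eligibility is settled.

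Blinding of the participant and the research assistant is a partial safeguard, but it does not name the person with the final say on eligibility. The protocol is also more than silent on concealment, because it tells the reader that none is needed.

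At stake is comparability of the arms at entry. Baseline adjustment can only partly repair selective entry, and with 50 women chance imbalance would make it hard to detect. It would affect all four comparisons under Hypotheses 3 and 4, those based on reaction times as well as craving and perceived stress.

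**Working it through.** The protocol gives no figure to reproduce on this point: no urn parameters, and no statement of how the three factors are combined. The check has four parts.

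**1. Is the next assignment predictable from the history?** Take a single urn with w balls per arm at the start and b balls added to the opposite arm after each assignment. Then P(next arm is AR) = AR balls / all balls. With w = 1 and b = 1, if the first woman goes to AR the urn holds 1 AR and 2 control balls, so the second woman goes to control with probability 2/3. With w = 10 and b = 1 the same step gives 11/21 = 0.52. The dependence that the protocol itself describes is what makes guessing possible.

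**2. How predictable over 50 women?** From the protocol: N = 50, roughly equal allocation, three binary factors. Assumed, because not stated: (w, b) as listed below; factor prevalences of 0.5/0.5/0.5 or 0.2/0.4/0.2; and a draw either from the most imbalanced of the woman's three urns or from the three pooled. The guesser knows every past assignment and the new woman's factor levels, and always names the likelier arm. Simulated share of correct guesses:

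| (w, b) | Single urn | Three factors, most imbalanced urn | Three factors, pooled |
|---|---|---|---|
| (10, 1) | 53.1% | 54.8-55.1% | 52.7-52.8% |
| (1, 1) | 55.1% | 60.3-61.0% | 55.5-55.9% |
| (1, 2) and (1, 3) | 55.5-55.6% | 61.5-62.8% | 56.0-56.7% |
| (0, 1) | 56.0% | 63.8-64.6% | 57.1-57.8% |

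The range is about 53-65%, against 50% when the history is hidden. In the three-factor runs the next arm was never certain when w was 1 or more, and was certain for about 2-9% of allocations when w = 0. The likelier arm had probability 0.70 or more in 0-18% of allocations.

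**3. What bias could follow?** Let a be the share of correct guesses, and s the difference in mean prognosis (in SD) between women admitted when AR is guessed and when control is guessed. The expected difference between arms is (2a - 1) x s. The documents give no value for s, so these are illustrations only:
- s = 0.5: (2 x 0.53 - 1) x 0.5 = 0.03 SD, up to (2 x 0.65 - 1) x 0.5 = 0.15 SD
- s = 0.1: 0.06 x 0.1 = 0.006 SD, up to 0.30 x 0.1 = 0.03 SD

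For scale, the standard error of a simple difference in means with 25 per arm is sqrt(2/25) = 0.28 SD. If an actual assignment could be seen before eligibility was confirmed, a would be 1 and the bias would equal s.

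**4. Who could hold the history?** Section V does not say who operates the urn or loads the condition onto the phone. Section IX, item 4 keeps subject lists and study progress on the investigator's computer, and lets the investigator retrieve smartphone data from the server after each assessment. Under AR the dot always replaces the neutral stimulus, while under control it is balanced (Section V, AR Intervention and Control Condition). Trial-level probe locations, if they are among the retrievable data, would therefore show the arm. The documents do not say that anyone uses these routes, and they describe no barrier to them.

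**The case against.** A reader might infer that the investigator can foresee each assignment. The documents do not support that. Nowhere do they say that the investigator runs the urn, sees its state or holds past assignments. The research assistant who makes the screening contact is blinded. Even full knowledge of the history leaves the draw random. Nor is an exposed urn as bad as an exposed fixed list, which would be 100% predictable.

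The room to steer is also limited. Age, the depression score, smoking history and CO-confirmed abstinence are measurable, and Section IX, item 3 has entrance criteria reviewed at the weekly study meeting. Consent review, intake, CO sample and baseline task already precede randomisation. The planned analysis (Section V, item 4) compares slopes, so a constant difference between arms at entry would largely drop out; only selection on later change would bias it. The stated goal is feasibility.

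All of this stands, and it limits the likely size of the problem. It does not rescue the sentence. Weekly review of criteria is not concealment, no order is given between the investigator's confirmation and the draw, and neither the investigator nor research staff other than the research assistant are covered by the blinding statement.

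**Conclusion.** The statement that concealment is unnecessary is wrong as written, and nothing elsewhere in the protocol supplies the missing procedure. Someone with the full history could guess the next arm correctly about 53-65% of the time instead of 50%. That range rests on assumed urn parameters, combination rules and factor prevalences. Whether anyone who decides on entry has that history is not stated: this is an unclosed gap, not a documented exposure.

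Selection bias at entry therefore cannot be ruled out, but its size cannot be estimated from the documents. Under history-based guessing it is probably modest: the illustrative values in SD units lie below the sampling error and do not carry over directly to the slope comparison. The correction is worth making because it is cheap and because the sentence weakens the credibility of any AR-versus-control result.

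**What to change.** In Section V, item 3:
- Delete the statement that concealment is not necessary.
- State that the urn is run by a central program, or by an existing team member who does not screen, consent or confirm eligibility, and give the urn parameters.
- Release only a masked task code, and only after consent, the investigator's eligibility confirmation (including the CO result) and the baseline visual probe task are recorded.
- Bar the investigator and all enrolling staff from the urn state, past assignments and probe-location data that reveal the arm.
- State whether the investigator is blinded.

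The cost is a small change of wording and access control; sample size, tasks and visits stay as they are. If enrolment has already taken place, the report should say who operated the urn and who could see assignments.

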Intervention Phase 1- Pregnancy: Following enrollment and randomization women will be asked to carry a smartphone as they go about their daily lives and complete 2 random assessments per day and an AB assessment every day for 2 weeks. Random assessments are comprised of questions assessing subjective states (see section d) and the AR (or control) procedure (described below). Data from each of the random assessments and AB assessments are transmitted in real-time allowing compliance to be assessed. If a participant responds to less than 2 random assessments on any study day a research assistant will contact the participant to encourage them to maintain compliance. At the end of the two weeks women will complete Visit 2 via Zoom and complete a post-training unmodified VP task and the Visit 2 assessments outlined in Table 1 and described below. If/once it is appropriate to resume in person visits, participants will be given the option of completing this visit in person at the research clinic.

All EMA procedures and VP tasks will be conducted on a smartphone running an application programmed by Terminal C, a Houston-based company.

Intervention Phase 2- Postpartum: Within 4 days of delivery, women will complete another VP task) and the Visit 3 assessments (Table 1). Participants will be asked to repeat the same procedure as in Phase 1, 2 random assessments per day and an AB assessment every day for 2 weeks. Once again at the end of 2 weeks they will schedule a visit via Zoom and complete an unmodified VP task and Visit 4 assessments. If/once it is appropriate to resume in person visits, participants will be given the option of completing this visit in person at the research clinic.

Post-treatment Visit: Follow-up visits, 5 and 6, will be scheduled 3 and 6 months, respectively, after phase 2. Women will complete an unmodified VP task and the assessments listed in Table 1. Again visits will be done via Zoom; if/once it is appropriate to resume in person visits, participants will be offered the option of completing these visits in person at the research clinic.

Assessments: A summary of the timing of assessments is shown in Table 1.

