- c) **Stress and anxiety outcomes (Visits 1-6):** The Perceived Stress Scale (PSS) will be used to assess stress at study visits and the short form (4-items) on the final daily smartphone assessment (see Table 2). The PSS has high reliability in a smoking cessation sample (Cronbach's $\alpha = .86$).⁶⁹ The state scale of the Spielberger State-Trait Anxiety Inventory (STAI-S)⁷⁰ (Cronbach's $\alpha = .89$)⁷¹ will be used to assess the impact of the transition stressor, arrival of new baby, on anxious mood state and to determine whether this is affected by AR. The Parenting Stress Index (PSI)-Short Form,⁷² an established measure of parent and child behaviors, can assess a wide range of parenting behaviors with good reliability (Cronbach's $\alpha = .83$). To assess for race-related stress among African American participants we will use the Index of Race-Related Stress-Brief Version (IRRS-B), a 22-item measure of race-related stress on cultural (Cronbach's $\alpha = .78$), institutional (Cronbach's $\alpha = .69$), and individual (Cronbach's $\alpha = .78$) racism.⁷³ Based on feedback from participants we have added a sentence to the introduction of the IRRS-B that acknowledges some of the language used in this questionnaire may be considered "dated" by some individuals and may not reflect current preferences for racial identity. To assess for cultural stress among Hispanic women we will use the Hispanic Stress Inventory-2 (HSI2), which has both an immigrant (Cronbach's $\alpha = .97$) and US-born version (Cronbach's $\alpha = .93$).⁷⁴ Social support as a measure of stress will be assessed on the final daily smartphone assessment via an adapted form of the 6-item version of the Social Support Questionnaire.⁷⁶
- d) **Smartphone Assessments:** Participants respond to the following items on 7-point Likert-type scales (1 = Strongly Disagree, 7 = Strongly Agree) according to how they feel "right now": **1) Craving** - A single item is used to assess craving for cigarettes; **2) Difficulty concentrating** - A single item will be administered to evaluate difficulty concentrating, used in previous EMA studies;⁷⁵ **3) Affect** - Items include: enthusiastic, happy, relaxed, bored, sad, anxious, angry. Two additional items assess overall mood

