AR Intervention: Women randomized to AR will be scheduled to complete 2 AR tasks per day. On the AR tasks, the dot always replaces the neutral picture (or word). There is a perfect correlation between picture type and dot location. Consistent with prior work each AR task will target both the initial orienting of attention (40 trials x 200 ms picture presentation) and the disengagement of attention (40 trials x 500 ms picture presentation).⁴² Based on pilot data, the mean duration of AR (and control) assessments is expected to be about 5-7 minutes. There will be 2 types of AR interventions, one targeting smoking-related stimuli and one targeting stress. The type of AR (smoking vs. stress) will alternate daily between the 2 AR tasks. For the smoking AR intervention we plan to use 15 picture sets of consisting of 20 culturally appropriate picture pairs (one smoking-related and one neutral) each. One picture set will be administered on each study day (days 0-14 in pregnancy and days 0-14 postpartum). For the stress AR intervention we plan to use 15 culturally appropriate word sets with 20 word pairs each. Word pairs consist of one emotionally neutral rated word (e.g. book) and an emotionally negative rated word (e.g. fear). We base this on the work of See et al., who demonstrated that AR was effective in inducing attentional avoidance of negative/stressful information (words), thus reducing anxiety related to a naturalistic stressor.⁴⁸ Again one word set will be administered on each study day (days 0-14 in pregnancy/postpartum). To facilitate compliance, a “delay” option will allow women to delay their response by 5 minutes, a “suspend” option will prevent the phone from presenting assessments for a specific time period, and a “make-up” option will allow women to complete trainings if they miss an AR or have technical difficulties (e.g. program crashes and prevents random assessment from being presented). The program is operational independent of internet connectivity, as it will run directly on the smartphone. Data will be stored on the phone and wirelessly backed-up on a server.

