Control Condition: The control task is identical to the AR task in number of tasks per day, number of trials per task (80 trials: 40 x 200ms and 40 x 500ms picture presentation) and the types of tasks: one containing smoking-related and neutral pictures (smoking control task), and one with stress-related and neutral words (stress control task). The only difference is that in the control task, the dot is equally likely to replace the smoking picture (or stress-related word) and the neutral picture (or word). There is a zero correlation between picture type and dot location, therefore there is no effect on AB. This type of control condition has been used in previous AR studies⁷⁷ and in our own pilot study, and ensures that: 1) the duration of AR and control training should not differ; 2) AR and control participants receive equal practice on the motoric aspects of the VP tasks; and 3) AR and control participants are exposed to the same smoking and neutral pictures or stress-related and neutral words. Note that, apart from the number of trials, the control task is the same as the standard VP task.

Attentional Bias Assessment: We will assess attentional bias using the standard VP task on the final random assessment of each day. Consistent with the AR task and prior work,⁴² the VP task will have stimulus presentation durations of 200 ms and 500 ms at each assessment. This will allow us to assess both the initial orienting of attention (20 trials x 200 ms) as well as the difficulty disengaging attention (20 trials x 500 ms), for a total of 40 trials.¹⁷ It will include a balance of both smoking and stress cues. Processing of reaction time data and computation of attentional bias will follow existing procedures.^{22,78} Reaction times (RTs) will be computed from trials with correct responses. We will compute attentional bias scores as the difference in RTs on trials where the probe replaced the smoking picture (or stress-related word) vs. trials where the probe replaced the neutral picture (or neutral word). Faster RTs on the former reflects an attentional bias towards the smoking picture/stress-related word, or vigilance. Faster RTs on

the latter reflects an attentional bias away from the smoking picture/stress-related word, or avoidance.

4. Statistical Considerations: Describe the statistical analyses that support the study design.

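### The staff-contact rule counts only the two daily training prompts, so a woman can miss every daily smartphone attentional-bias assessment without triggering a contact

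*Combined protocol and SAP*

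**What the plan says.** The relevant text is in Section V, item 3 (Research Plan), item 4 (Statistical Considerations) and Section X, item 2 (Payments).

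- **Daily schedule (Intervention Phase 1).** Women are to "complete 2 random assessments per day and an AB assessment every day for 2 weeks". The content of the first kind is defined: "Random assessments are comprised of questions assessing subjective states (see section d) and the AR (or control) procedure". Phase 2 uses the same schedule: "Participants will be asked to repeat the same procedure as in Phase 1, 2 random assessments per day and an AB assessment every day".
- **Compliance data (Intervention Phase 1).** "Data from each of the random assessments and AB assessments are transmitted in real-time allowing compliance to be assessed".
- **Contact rule (the next sentence).** "If a participant responds to less than 2 random assessments on any study day a research assistant will contact the participant".
- **Make-up option (AR Intervention).** This "option will allow women to complete trainings if they miss an AR" or have technical problems. No make-up is stated specifically for the AB assessment.
- **Where the daily outcomes are collected.** Under Attentional Bias Assessment: "We will assess attentional bias using the standard VP task on the final random assessment of each day". Under Assessments, part c, stress is measured by "the short form (4-items) on the final daily smartphone assessment".
- **Which outcomes these are (Table 2).** Hypotheses 3a, 4a and 4b are each tied to a smartphone measure taken once a day. Craving is taken three times a day and the intervention is given twice.
- **Payment.** $2 per smartphone assessment plus $8 for each fully completed week, up to $200 for 84 assessments.

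**The concern.** The protocol receives two streams of compliance data but acts on only one. The stream it acts on delivers the training. The other carries the daily attentional-bias outcome and, apparently, the daily stress outcome. A woman who does both trainings and skips the third prompt is compliant under the rule, yet adds nothing to the smartphone analyses of Hypotheses 3a and 4a.

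This matters because the main analysis compares slopes over assessment number between arms, so the repeated daily records are its raw material. The plan already concedes limited power. It relies on mixed models to cope with missing records and names no sensitivity analysis for missingness that depends on the outcome. Avoidable loss of these records is therefore worth preventing while the trial is running.

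**Working it through.** **1. Reproduce the plan's own count.** Inputs: 2 random assessments and 1 AB assessment per day, 14 days per phase, 2 phases (Section V.3); 84 assessments, $2 each, $8 per complete week, $200 maximum (Section X.2).

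- Days: 14 × 2 = 28.
- Prompts: (2 + 1) × 28 = 84, as stated.
- Smartphone payment: 84 × $2 + 4 × $8 = $168 + $32 = $200, as stated.
- Total payment: $20 + $200 + 4 × $20 + 2 × $50 = $400, as stated.

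The figures agree with three prompts a day, as does Table 2 (craving 3, intervention 2).

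**2. Apply the contact rule to a day on which both trainings are done and the AB prompt is missed.** Two sections describe the prompts differently: Intervention Phase 1 lists the AB assessment separately, while Attentional Bias Assessment places it on the last random assessment. Three readings are possible.

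| Reading | Random assessments completed | Contact? | Total prompts | Smartphone payment |
|---|---|---|---|---|
| A: 2 random plus a separate AB | 2 of 2 | No | 84 | $200 |
| B: 3 random, AB on the third | 2 of 3 | No (2 is not fewer than 2) | 84 | $200 |
| C: 2 random, AB on the second | 1 of 2 | Yes | 2 × 28 = 56 | 56 × $2 + $32 = $144 |

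Reading C shows a day with the AB-bearing prompt missed. It would close the gap, but it contradicts both the 84 and the $200. The two readings that fit the stated figures leave the gap open.

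**3. Size of the gap under Readings A and B.** A woman who skips only the AB prompt every day:

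- completes 2 × 28 = 56 prompts, and 56/84 = 66.7%;
- supplies 0 of 28 daily AB records;
- supplies 0 of 28 daily PSS records, if the last smartphone assessment of the day is the AB prompt;
- triggers contact on 0 of 28 days.

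If a missed AB assessment also triggered contact, the same pattern would do so on all 28 days.

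**4. What payment does.** She earns 56 × $2 = $112 and no weekly bonus. She forfeits 28 × $2 + 4 × $8 = $88, which is 44% of $200.

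**5. Illustrative effect on precision.** The plan gives no completion rates, so these are assumptions. At 80% completion a woman gives 28 × 0.8 = 22.4 records; at 60%, 28 × 0.6 = 16.8; at 50%, 14. If day-to-day noise dominates and records are lost evenly over time, the standard error scales with one over the square root of the number of records:

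- 60% against 80%: √(0.8/0.6) = 1.15, a rise of about 15%.
- 50% against 80%: √(0.8/0.5) = 1.26, a rise of about 26%.

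These are upper ends for those completion rates. If women's own slopes differ substantially, that variation is not reduced by having more records per woman, and the rise shrinks towards zero.

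**The case against.** The strongest reply is that the daily AB assessment is not unprotected and that the trial does not depend on it alone.

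- **Visit measures.** Table 1 schedules the standard VP task and the PSS at Visits 1 to 6, and the plan also analyses attentional bias from the visits. This stands. A reader might infer that a woman could lose every outcome for Hypotheses 3a, 4a and 4b; the documents do not support that. The exposure is confined to the daily smartphone records. The visits give at most 6 points against 28, however, and Table 2 defines these outcomes as smartphone measures.
- **Payment and tallying.** Losing $88 of $200 is a real deterrent. Because payment is per assessment and made at Visits 2 and 4, staff must count completed prompts by then. This also stands, so it would be wrong to say that staff could have no warning. But a count at Visit 2 comes after the 14 days of Phase 1. The protocol also adds staff contact on top of payment for training and gives no reason for leaving out the outcome prompt.
- **The AB task may be one of two random assessments.** Then missing it would trigger contact. The wording under Attentional Bias Assessment permits this, but the stated 84 assessments and $200 do not.
- **The make-up option may extend to the AB assessment.** It covers technical failures affecting random assessments, and one section calls the AB prompt a random assessment. The text is open here, so the contact rule is the firmer point.
- **The harm is conjectural.** It is tempting to say that skipped prompts fall on stressful or high-craving evenings and so bias the result. That is plausible, but the documents say nothing about when or why prompts are skipped. Nor do they suggest differential loss: the rule is the same in both arms and the research assistant is blinded. Likewise, nothing shows that the suspend option falls mainly on the last prompt.
- **It is an operational choice in a small feasibility study.** This is fair as to severity. It does not explain why AB compliance data are collected but left out of the rule.

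**Conclusion.** The concern holds for the daily smartphone outcomes. On either reading that fits the plan's 84 assessments, a woman can complete 67% of prompts, give none of the 28 daily AB records for Hypotheses 3a and 4a, and never meet the contact trigger. The same applies to the 28 daily PSS records for Hypothesis 4b only if the last smartphone assessment is the AB prompt. The stress and attentional-bias sections together suggest this, but the schedule does not state it.

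The gap itself follows from the text and needs no assumption about behaviour. Its consequence does: a 15% rise in standard error rests on assumed completion of 60% rather than 80% and on day-to-day noise dominating, and outcome-dependent missingness is possible but undocumented. This is a worthwhile, inexpensive improvement. It does not invalidate the trial, and it does not show bias between arms.

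**What to change.** 1. **Define the daily prompts once.** Reconcile Intervention Phase 1 with Attentional Bias Assessment so that both describe the same three prompts: two training assessments and one AB assessment. State which prompt carries the 4-item PSS.
2. **Change the contact trigger, for both phases and both arms.** Suggested wording: *A research assistant will contact the participant if, on any study day, she misses the AB assessment or completes fewer than 2 training assessments.*
3. **Optional.** State whether a missed AB assessment may be made up. If so, time-stamp it and apply the same rule in both arms. This is more debatable than the trigger, because it changes when the momentary sample is taken.

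**Cost.** A wording amendment, a compliance flag on data already transmitted, and a few more reminder contacts by existing staff. Participants carry slightly more burden, including in the two weeks after delivery. The optional make-up would also need a small application setting.
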